10.4. Appendix 4: Prohibited Concomitant Medications

This list of medications is **not all-inclusive**; if necessary, please contact the medical monitor for any questions regarding (a) medication(s).

Please refer to the local prescribing information of the participant's SSRI/SNRI for information regarding prohibited concomitant medications.

Except where specifically noted (and as applicable per randomly assigned study intervention arm), the prohibited medications listed in the following table are prohibited from 1 week (or 5 half-lives, whichever is longer) prior to the first dose of study intervention (ie, esketamine nasal spray or quetiapine XR, both in combination with continuing SSRI/SNRI) until after the last dose of study intervention. Before prescribing any concomitant medications, an experienced clinician needs to evaluate the medical need and estimated risk for additional side effects. Additionally, the risk of cumulative increase in side effects (eg, sedation, QT-prolongation, weight gain) should be avoided.

Note in the following table: N, prohibited; Y, permitted with restrictions (please refer to the column labeled "Comments" for additional guidance).

	Episodic			_
	Use (As	Continuous		Reason for
Drug Class	Needed)	Use	Comments	Prohibition
Attention deficit	Ν	Y	Can be continued but must not be	Safety
hyperactivity disorder			taken within 12 hours prior to the nasal	
(ADHD) medications (eg,			treatment session or for 2 hours after	
atomoxetine, guanfacine)			the nasal treatment session for	
			participants in the esketamine	
			treatment arm.	
Amantadine	N	N		PD interaction
Anorexiants	Ν	Ν		Safety
(eg, phentermine,				
phendimetrazine)				
Anti-cholinergic medications	Ν	Ν	As quetiapine has a moderate to strong	Safety
(eg, Atropine, Benztropine,			affinity for several muscarinic receptor	
Biperiden)			subtypes, concomitantly used with	
			other medicines with anti-cholinergic	
			effects can contributes to occurrence of	
			ADR reflecting anti-cholinergic effects	
			(eg, decreased intestinal motility and	
			risk for intestinal obstruction)	
Anticholinesterase inhibitors	Ν	N		Participant
				population is
				excluded
Anticonvulsants	Ν	N	Participants with seizures are	Safety and PD
			excluded. Use as adjunctive treatment	interaction
			for MDD is prohibited.	
			- Note: Anticonvulsants used for	
			indications other than seizures may	
			be allowed (eg, valproate for	
			migraine; pregabalin).	

	Episodic	~		-
Drug Class	Use (As Needed)	Continuous	Commonts	Reason for Prohibition
Antidepressants (ADs)	Neeueu)	N N	- If a participant is taking a	Safety and PD
(other than continuing	11	11	monoamine oxidase inhibitor	interaction
SSRI/SNRI as described in			(MAOI) at screening, there must be a	
Section 6.1.3)			minimum wash-out interval of	
			2 weeks prior to the first dose of	
			study intervention.	
			- Even if used for indications other	
			than MDD (eg, trazodone for sleep),	
			the use of any ADs other than	
			specified as study intervention is not	
			permitted during treatment with	
			study intervention.	
Antipsychotics	N	N	Durch ihida diarridhina 12 harrana miranda dha	PD interaction
Benzodiazepines (at dosages	Ŷ	Ŷ	Prohibited within 12 nours prior to the	Safety and PD
equal to of less than the equivalent of 4 mg/day			treatment session for participants in	Interaction
lorazenam) and non-			the esketamine arm	
benzodiazenine sleening			the esketamine arm.	
medication (including)			The need for sleep medication should	
zolpidem, zaleplon.			be evaluated critically and additional	
eszopiclone, and ramelteon)			sedation should be taken in	
1 , ,			consideration.	
Benztropine	Y	Ν	Prohibited if use is continuous.	Safety and PD
				interaction
Chloral hydrate, melatonin,	Ν	Ν		Safety and PD
Valerian Classidina	V	V		interaction
Clonidine	Ŷ	Ŷ	allowed.	
Corticosteroids (systemic)	Y	N	Inhaled, nasal, topical, and ophthalmic	PD interaction
			steroids are not prohibited. Nasally	
			administered corticosteroids should	
			not be used from 1 hour prior to each	
			esketamine nasal spray administration.	
			Intermittent IM/IV/PO corticosteroids	
			are permitted with sponsor approval	
			(chronic use prohibited).	
Cough/cold preparations/	Y	Y	Nasally administered decongestants	Safety and PD
nasal solutions containing			(vasoconstrictors) should not be used	interaction
vasoconstrictors,			from 1 hour prior to each esketamine	
decongestants			nasal spray administration.	
			Pseudoephedrine-containing oral	
			products should not be used within	
			12 hours prior to a nasal treatment	
			session.	

	Episodic			
	Use (As	Continuous		Reason for
Drug Class	Needed)	Use	Comments	Prohibition
CYP3A4 inducers - potent	N	N	Participants may not take a known potent inducer of hepatic CYP3A activity within 2 weeks of the first administration of study intervention until at least 24 hours after the last dose of study intervention. Examples (not all-inclusive): amiodarone, efavirenz, nevirapine, barbiturates, carbamazepine, glucocorticoids, modafinil, oxcarbazepine, phenobarbital, phenytoin, rifabutin, rifampin, and St. John's wort	РК
CYP3A4 inhibitors	Ν	N	Participants may not take a known potent inhibitor of hepatic CYP3A activity within 2 weeks of the first administration of study intervention until at least 24 hours after the last dose of study intervention. Examples (not all-inclusive): erythromycin, clarithromycin, nefazodone, HIV-protease inhibitors, azole-antifungal agents; grapefruit juice.	
Dextromethorphan	Ν	N	·	PD interaction
Diphenhydramine	Y	N	Prohibited within 12 hours prior to the start of each nasal treatment session in the esketamine arm. The need for sleep medication should be evaluated critically, and additional sedation should be taken into consideration.	Safety
Ketanserin	Ν	N		Safety
Lithium	Ν	N		PD interaction

	Episodic Use (As	Continuous		Reason for
Drug Class	Needed)	Use	Comments	Prohibition
Medications that cause	N	N	Reported interaction with quetianine	Safety
electrolyte imbalance or OT-	11	1,	reported interaction with quotaphie.	Survey
prolongation (corrected				
according to Fridericia's				
formula (OTcF): >450 msec				
(males); \geq 470 msec				
(females) eg,				
Antiarrhythmics (quinidine,				
procainamide, disopromide,				
dofetilide, ibutilide, sotalol),				
Antihistamines (terfenadine,				
astemizole), Neuroleptic,				
(haloperidol, droperidol,				
thioridazine,				
chlorpromazine), Antibiotics				
(levofloxacin, moxifloxacin,				
erythromycin,				
clarithromycin),				
Antimalarials (quinine,				
halofantrine), Antiprotozoal				
(pentamidine), Antifungal				
(azole group)	N	N		
Memantine	N	IN N		PD interaction
Methyldopa	IN	IN		Safety and PD
Matawasina	N	N		Interaction
Metyrosine	IN	IN		salely and PD
Non steroidal anti	v	v	Participants should not take within	Interaction
inflammatory drugs	1	1	24 hours before biomarker blood	
(NSAIDs)			sample collection at Day 1 and Week 8	
(110/1103)			visits.	
Non-vitamin K antagonist	N	N		Safety
oral anticoagulation agents	1.	1.		~
(eg. dabigatran, rivaroxaban,				
apixaban)				
Opioids	Ν	N	Note: With Sponsor approval, brief	PD interaction
1			treatment with opiates may be allowed	
			for treatment of acute injuries etc.	
Psychostimulants	N	Y	Prescribed psychostimulants taken for	Cardiovascular
(eg, amphetamines,			indications other than MDD can be	safety
methylphenidate)			continued but must not be taken:	
			• Within 12 hours prior to the	
			esketamine nasal treatment session	
			or for 2 hours after the nasal	
			treatment session in the esketamine	
			arm.	
			• Within 12 hours prior to visits in	
			the comparator arm (minimize	
			differences in study intervention	
	) ,		arms related to PROs)	
Reserpine	N	N		PD interaction
Scopolamine	N	N		PD interaction
St. John's wort	N	N		PD interaction
				and PK

Drug Class	Episodic Use (As Needed)	Continuous Use	Comments	Reason for Prohibition
Thyroid hormone	N	Y		Safety
supplement for treatment of				
thyroid condition only (not				
for depression)				
Thyroxine/triiodothyronine	Ν	N		PD interaction
(T3), thyroid hormone				
prescribed for depression				
Warfarin	N	N		Primary
				condition where
				used is
				excluded

Abbreviations: CYP=cytochrome P450; HIV= human immunodeficiency virus; IM=intramuscular;

IV=intravenous; MDD=major depressive disorder; N=Prohibited; PD=pharmacodynamic; PK=pharmacokinetic; PO=oral; PRO=patient-reported outcomes; SSRI=selective serotonin reuptake inhibitor; SNRI=serotonin-norepinephrine reuptake inhibitor; Y=permitted, with restrictions (please refer to the column labeled "Comments" for additional guidance).

10.5. Appendix 5: Adverse Events: Definitions and Procedures for Recording, Evaluating, Follow-up, and Reporting

ADVERSE EVENT DEFINITIONS AND CLASSIFICATIONS

Adverse Event

An AE is any untoward medical occurrence in a clinical study participant administered a medicinal (investigational or non-investigational) product. An AE does not necessarily have a causal relationship with the intervention. An AE can therefore be any unfavorable and unintended sign (including an abnormal finding), symptom, or disease temporally associated with the use of a medicinal (investigational or non-investigational) product, whether or not related to that medicinal (investigational or non-investigational) product. (Definition per ICH)

This includes any occurrence that is new in onset or aggravated in severity or frequency from the baseline condition, or abnormal results of diagnostic procedures, including laboratory test abnormalities.

Note: The sponsor collects AEs starting with the signing of the ICF (refer to All Adverse Events under Section 8.3.1, Time Period and Frequency for Collecting Adverse Events and Serious Adverse Events Information, for time of last AE recording).

For combination products with a device constituent, adverse events include those resulting from insufficient or inadequate instructions for use, deployment, implantation, installation, or operation, or any malfunction of the device. It includes any adverse event resulting from use error or from intentional misuse of the investigational device.

Serious Adverse Event

A SAE based on ICH and European Union Guidelines on Pharmacovigilance for Medicinal Products for Human Use is any untoward medical occurrence that at any dose:

- Results in death
- Is life threatening

(The participant was at risk of death at the time of the event. It does not refer to an event that hypothetically might have caused death if it were more severe.)

- Requires inpatient hospitalization or prolongation of existing hospitalization
- Results in persistent or significant disability/incapacity
- Is a congenital anomaly/birth defect
- Is a suspected transmission of any infectious agent via a medicinal product
- Is Medically Important*

* Medical and scientific judgment should be exercised in deciding whether expedited reporting is also appropriate in other situations, such as important medical events that may not be immediately life threatening or result in death or hospitalization but may jeopardize the participant or may require intervention to prevent one of the other outcomes listed in the definition above. These should usually be considered serious.

If a serious and unexpected AE occurs for which there is evidence suggesting a causal relationship between the study intervention and the event (eg, death from anaphylaxis), the event must be reported as a serious and unexpected suspected adverse reaction even if it is a component of the study endpoint (eg, all-cause mortality).

For combination products with a device constituent, serious adverse events include adverse device effects that resulted in any of the consequences characteristic of a serious adverse event.

Unlisted (Unexpected) Adverse Event/Reference Safety Information

An AE is considered unlisted if the nature or severity is not consistent with the applicable product reference safety information. For esketamine nasal spray, the expectedness of an AE will be determined by whether or not it is listed in the IB. For quetiapine XR and the SSRIs/SNRIs, the expectedness of an AE will be determined by whether or not it is listed in the SmPC (if applicable).

ATTRIBUTION DEFINITIONS

Assessment of Causality

The causal relationship to study intervention is determined by the investigator. The following selection should be used to assess all AEs.

Related

There is a reasonable causal relationship between study intervention administration and the AE.

Not Related

There is not a reasonable causal relationship between study intervention administration and the AE.

The term "reasonable causal relationship" means there is evidence to support a causal relationship.

SEVERITY CRITERIA

An assessment of severity grade will be made using the following general categorical descriptors:

Mild: Awareness of symptoms that are easily tolerated, causing minimal discomfort and not interfering with everyday activities.

Moderate: Sufficient discomfort is present to cause interference with normal activity.

Severe: Extreme distress, causing significant impairment of functioning or incapacitation. Prevents normal everyday activities.

The investigator should use clinical judgment in assessing the severity of events not directly experienced by the participant (eg, laboratory abnormalities).

SPECIAL REPORTING SITUATIONS

Safety reporting situations for a sponsor study intervention in an interventional study that may require expedited reporting or safety evaluation include, but are not limited to:

- Overdose of a sponsor study intervention
- Suspected abuse/misuse of a sponsor study intervention
- Accidental or occupational exposure to a sponsor study intervention
- Any failure of expected pharmacologic action (ie, lack of effect) of a sponsor study intervention
- Unexpected therapeutic or clinical benefit from use of a sponsor study intervention
- Medication error, intercepted medication error, or potential medication error involving a Johnson & Johnson medicinal product (with or without patient exposure to the Johnson & Johnson medicinal product, eg, product name confusion, product label confusion, intercepted prescribing or dispensing errors)
- Exposure to a sponsor study intervention from breastfeeding

Special reporting situations should be recorded in the eCRF. Any special reporting situation that meets the criteria of a SAE should be recorded on the SAE page of the eCRF.

PROCEDURES

All Adverse Events

All AEs, regardless of seriousness, severity, or presumed relationship to study intervention, must be recorded using medical terminology in the source document and the eCRF. Whenever possible, diagnoses should be given when signs and symptoms are due to a common etiology (eg, cough, runny nose, sneezing, sore throat, and head congestion should be reported as "upper respiratory infection"). Investigators must record in the eCRF their opinion concerning the relationship of the AE to study therapy. All measures required for AE management must be recorded in the source document and reported according to sponsor instructions.

For all studies with an outpatient phase, including open-label studies, the participant must be provided with a "wallet (study) card" and instructed to carry this card with them for the duration of the study indicating the following:

- Study number
- Statement, in the local language(s), that the participant is participating in a clinical study
- Investigator's name and 24-hour contact telephone number
- Local sponsor's name and 24-hour contact telephone number (for medical personnel only)
- Site number
- Participant number
- Any other information that is required to do an emergency breaking of the blind

Serious Adverse Events

All SAEs that have not resolved by the end of the study, or that have not resolved upon discontinuation of the participant's participation in the study, must be followed until any of the following occurs:

- The event resolves
- The event stabilizes
- The event returns to baseline, if a baseline value/status is available
- The event can be attributed to agents other than the study intervention or to factors unrelated to study conduct
- It becomes unlikely that any additional information can be obtained (participant or health care practitioner refusal to provide additional information, lost to follow-up after demonstration of due diligence with follow-up efforts)

Suspected transmission of an infectious agent by a medicinal product will be reported as a SAE. Any event requiring hospitalization (or prolongation of hospitalization) that occurs during the course of a participant's participation in a study must be reported as a SAE, except hospitalizations for the following:

- Hospitalizations not intended to treat an acute illness or AE (eg, social reasons such as pending placement in long-term care facility)
- Surgery or procedure planned before entry into the study (must be documented in the eCRF). Note: Hospitalizations that were planned before the signing of the ICF, and where the underlying condition for which the hospitalization was planned has not worsened, will not be considered SAEs. Any AE that results in a prolongation of the originally planned hospitalization is to be reported as a new SAE.
- For convenience the investigator may choose to hospitalize the participant for the duration of the intervention period.

The cause of death of a participant in a study, whether or not the event is expected or associated with the study intervention, is considered a SAE.

CONTACTING SPONSOR REGARDING SAFETY

The names (and corresponding telephone numbers) of the individuals who should be contacted regarding safety issues or questions regarding the study are listed in the Contact Information page(s), which will be provided as a separate document.

PRODUCT QUALITY COMPLAINT HANDLING

A product quality complaint (PQC) is defined as any suspicion of a product defect related to manufacturing, labeling, or packaging, ie, any dissatisfaction relative to the identity, quality, durability, reliability, or performance of a distributed product, including its labeling, drug delivery system, or package integrity. A PQC may have an impact on the safety and efficacy of the product. In addition, it includes any technical complaints, defined as any complaint that indicates a potential

quality issue during manufacturing, packaging, release testing, stability monitoring, dose preparation, storage or distribution of the product or the drug delivery system.

This definition includes any PQC related to a device constituent in a combination product, including those used in the administration of the study intervention or the comparator. A device deficiency is an inadequacy of a device with respect to its identity, quality, durability, reliability, safety, or performance. Device deficiencies include malfunctions, use errors, and inadequate labeling.

Procedures

All initial PQCs must be reported to the sponsor by the study-site personnel within 24 hours after being made aware of the event.

A sample of the suspected product should be maintained under the correct storage conditions until a shipment request is received from the sponsor.

Contacting Sponsor Regarding Product Quality

The names (and corresponding telephone numbers) of the individuals who should be contacted regarding product quality issues are listed in the Contact Information page(s), which will be provided as a separate document.

Esketamine-Specific Reporting Requirements for PQCs

Additional PQC reporting requirements for esketamine nasal spray will be provided in a separate document.

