5. STUDY POPULATION

The study will be conducted internationally. Screening for eligible participants will be performed within 14 days before administration of the study intervention. Refer to Section 5.4, Screen Failures for conditions under which the repeat of any screening procedures are allowed.

The inclusion and exclusion criteria for enrolling participants in this study are described below. If there is a question about these criteria, the investigator must consult with the appropriate sponsor representative and resolve any issues before enrolling a participant in the study. Waivers are not allowed.

For a discussion of the statistical considerations of participant selection, refer to Section 9.2, Sample Size Determination.

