See Section 8.2.4, Clinical Safety Laboratory Assessments for additional information on the timing of the urine drug screen at baseline (Day 1) visit.

- 20. has uncontrolled diabetes mellitus, as evidenced by HbA1c >9% in the medical records, routine laboratory test, or history in the 3 months prior to baseline; or diabetic ketoacidosis, hyperglycemic coma, or severe hypoglycemia with loss of consciousness evaluated from medical history.
- 21. has untreated glaucoma, current penetrating or perforating eye injury, brain injury, hypertensive encephalopathy, intrathecal therapy with ventricular shunts, or any other condition associated with increased intracranial pressure or increased intraocular pressure or planned eye surgery evaluated from medical history.
- 22. has any anatomical or medical condition that, per the investigator's clinical judgment based on assessment, may impede delivery or absorption of esketamine nasal spray.
- 23. has a history of malignancy within 5 years before baseline (exceptions are squamous and basal cell carcinomas of the skin and carcinoma in situ of the cervix, or malignancy that, in the opinion of the investigator, with concurrence with the sponsor's medical monitor, is considered cured with minimal risk of recurrence).
- 24. has known allergies, hypersensitivity, intolerance, or contraindications to esketamine/ketamine, quetiapine XR, and/or any excipients.^{15,28}
- 25. has taken any prohibited therapies that would not permit dosing on Day 1 as defined in protocol (Section 6.5, Concomitant Therapy and Appendix 4, Prohibited Concomitant Medications).
- 26. is taking a total daily dose of benzodiazepines greater than the equivalent of 4 mg/day of lorazepam on Day 1.
- 27. has been included in any esketamine or ketamine clinical study, or has received an investigational drug (including investigational vaccines) or used an invasive investigational medical device within 60 days before the start of the screening phase, or

has participated in 2 or more MDD or other psychiatric condition clinical interventional studies (with different investigational medication) in the previous 1 year before baseline, or is currently enrolled in an investigational interventional study.

- 28. any condition for which, in the opinion of the investigator, participation would not be in the best interest of the participant (eg, compromise the well-being) or that could prevent, limit, or confound the protocol-specified assessments.

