6.5. Concomitant Therapy

Prestudy non-AD therapies administered up to 30 days before screening must be recorded.

All consecutive treatment(s) with AD taken at an adequate dosage (based on antidepressive dosages from label) for adequate duration of at least 6 weeks, including adjunctive treatment for MDD, during the current moderate to severe depressive episode (ie, including those taken more than 30 days prior to screening) will be documented at screening (see Appendix 3, Regulatory, Ethical, and Study Oversight Considerations: Source Documents).

Participants who were taking \leq 50 mg/day of quetiapine (XR or immediate-release) at screening (eg, for insomnia or agitation) are allowed to enter the study provided it is washed-out by at least 7 days prior to randomization.

Participants who are taking combination ADs and/or augmentation (other than quetiapine XR, which is exclusionary at doses >50 mg/day for the current moderate to severe depressive episode) at screening must stop all AD treatment, including any augmenting substances, prior to randomization on Day 1, except the SSRI/SNRI to be continued.

• For participants taking combination therapy with an SSRI/SNRI and an antipsychotic medication or any other augmenting substances, the antipsychotic medication and other augmenting substances need to be down-titrated and stopped prior to randomization. The investigator should follow the SmPCs (or local equivalents, if applicable) for all treatments that need to be discontinued. Although not standard practice, should a participant be taking more than 1 SSRI/SNRI at screening, the investigator should choose the one most likely to have a beneficial effect on depressive symptoms when combined with intranasal esketamine or augmented with quetiapine XR, based on individual participant characteristics. The choice of the SSRI/SNRI to continue should take into account potential side-effects when given in combination with quetiapine XR, should the patient be randomized to that arm.

A list of prohibited concomitant medications is provided in Appendix 4 as general guidance for the investigator (but is not all-inclusive). Investigators should refer to the applicable SmPCs (or local equivalent, if applicable) for prohibited concomitant medications for the continuing SSRI/SNRI. Any prescribed medications will not be discontinued without the agreement of the participant's treating physician.

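### Protocol Appendix 4 gives two different codes for as-needed benztropine (prohibited in the anti-cholinergic row, permitted in its own row) and does not say which applies: a minor inconsistency to correct

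*Protocol*

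**What the plan says.** Protocol Section 10.4 (Appendix 4) codes each drug class separately for episodic and continuous use. Its legend reads "N, prohibited; Y, permitted with restrictions", with the restrictions given in the comments column.

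- **Anti-cholinergic row.** The examples begin "eg, Atropine, Benztropine". Both columns are coded N and the reason given is safety. The comment explains that quetiapine itself acts on muscarinic receptors, so a further anti-cholinergic drug can contribute to reactions such as reduced gut motility and a risk of obstruction.
- **Benztropine row.** Episodic use is coded Y and continuous use N. The whole comment is "Prohibited if use is continuous". No arm is mentioned.
- **Lead-in.** The sentence that sets the prohibition period opens "Except where specifically noted (and as applicable per randomly assigned study intervention arm". It starts the period 1 week, or 5 half-lives if longer, before the first dose of study intervention.
- **Status of the list.** Section 6.5 says that the list is "provided in Appendix 4 as general guidance for the investigator (but is not all-inclusive".

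**The concern.** The legend gives N and Y opposite meanings, so the same as-needed use of the same drug is barred by one row and allowed by another. The rows do not sit next to each other, and a site that looks the drug up by name finds a clear permission.

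Two things are at stake:

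- **Participant safety in the comparator arm.** The protocol's own reason for the prohibition is the combination with quetiapine, and the benztropine row as written allows that combination.
- **Consistent handling across sites.** Section 6.5 requires the sponsor to be told when a prohibited therapy is given. Exclusion criterion 25 bars anyone who "has taken any prohibited therapies that would not permit dosing on Day 1 as defined in protocol". Whether as-needed benztropine counts under either rule depends on the row a site follows.

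**Working it through.** No arithmetic applies. The check sets the two rows side by side and then looks for text that ranks or separates them.

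| Use of benztropine | Anti-cholinergic row | Benztropine row | Agreement |
|---|---|---|---|
| As needed | N | Y | conflict |
| Continuous | N | N | none needed: same code |

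**1. Are the codes legible?** Yes. The benztropine comment confirms its own coding, because a comment that bars only continuous use makes sense only if episodic use is allowed.

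**2. Does the lead-in rank the rows?** It allows for exceptions that are specifically noted. A row for benztropine alone could be such an exception to the class row. However, the class row also names benztropine, and the clause belongs to a sentence about the prohibition period. It does not mention precedence between rows.

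**3. Does the lead-in separate the rows by arm?** It refers to applicability by randomized arm, and the class-row comment is about quetiapine. One could therefore apply the class row to the comparator arm and the benztropine row to the esketamine arm. Neither row says this. Other rows do name the arm, for example diphenhydramine: "Prohibited within 12 hours prior to the start of each nasal treatment session in the esketamine arm".

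**4. Would an arm-based reading work in practice?** Only after randomization. The prohibition begins at least 1 week before the first dose, while Section 4.1 assigns the arm on Day 1. For that week or more, no site knows which arm's rule would apply.

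**5. Is there a rule elsewhere?** Sections 6.5 and 8.2 refer to the list as guidance and give no order of precedence. The amendment summary records that anti-cholinergic medications were added to the table following health authority requests. That may explain how two entries came to coexist, but it does not say which one the sponsor intends.

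**The case against.** The best case for leaving the text alone has four parts.

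- **A reconciling reading exists.** A dedicated row is more specific than an example in a class row, and the lead-in provides for specific exceptions and for applicability by arm. This stands as a possible reading. A reader might go further and infer that the benztropine row cannot be limited by arm, because the table always names the arm when it means one. The documents do not support that. The pseudoephedrine restriction is tied to nasal treatment sessions, so it concerns esketamine only, yet it names no arm. The row on QT-prolonging drugs also rests on a quetiapine interaction without naming an arm. In addition, the arm wording in the diphenhydramine row limits a 12-hour timing rule, not the permission itself. The accurate statement is that an arm limit for benztropine is not stated.
- **Safeguards exist.** Appendix 4 asks an experienced clinician to weigh need and added side-effect risk before any concomitant prescription, warns against cumulative side effects, and offers the medical monitor for questions. Sites also receive the quetiapine XR product information. These measures lower the risk. The monitor helps only a site that notices the conflict, and no safeguard says which row applies.
- **Eligibility is largely covered.** On any question about the criteria, Section 5 requires that "the investigator must consult with the appropriate sponsor representative and resolve any issues before enrolling a participant in the study". This stands, again provided the site sees that there is a question.
- **Traceability is preserved.** Section 6.5 has all therapies recorded in the eCRF, so exposure can be found whichever row was followed. Major deviations are defined in a separate document (SAP Section 6.4) that is not available here. What is shown is uncertainty about sponsor notification, not misclassification in an analysis.

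**Conclusion.** The inconsistency is real and the table is wrong as written, but it is minor and belongs at the lowest severity. It concerns one drug and one of two use columns, in a list described as general guidance. Continuous use is prohibited by both rows.

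The safety consequence is confined to the comparator arm, because the stated reason is additive effect with quetiapine. A reader might take the planned size of that arm, 311 of 622 participants, as the scale of the problem. It is only the arm size. The documents give no expected rate of benztropine use, so the number exposed cannot be estimated. Nor should the point be read as a flaw in the trial's design or analysis: no endpoint, sample size or planned analysis depends on it.

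The conclusion assumes that no site-level instruction outside the protocol and SAP already settles which row applies.

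**What to change.** Make the two entries agree. The default should be to delete the benztropine row or code it N in both columns, since that follows the safety reason already given in the anti-cholinergic row. If the sponsor means to allow as-needed use in the esketamine arm only, remove benztropine from the anti-cholinergic examples and write the arm limit into the benztropine row. In that case, also say what applies before randomization.

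The cost is a correction to one table, by clarification letter to sites or within a protocol amendment. Visits, data collection, sample size and analysis stay as they are.
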